## LIST OF ABBREVIATIONS

---

AE	Adverse event
ALT	Alanine aminotransferase
AP	Alkaline phosphatase
ASP	Application Service Provider
AST	Aspartate aminotransferase
BUN	Blood urea nitrogen
CC	Conventional cigarette
CDC	Center for Disease Control and Prevention
CFR	Code of Federal Regulations
CO	Carbon monoxide
CRF	Case report form
CRM	Customer relationship management
ECG	Electrocardiogram
EOS	End of Study
FDA	Food and Drug Administration
FTND	Fagerström test for nicotine dependence
GCP	Good Clinical Practice
HCG	Human chorionic gonadotropin
ICF	Informed consent form
ICH	International Conference on Harmonisation
IRB	Institutional Review Board
Kg	Kilograms
Lbs	pounds
QTc	Corrected QT interval
mCEQ	Modified Cigarette Evaluation Questionnaire.
MCH	Mean corpuscular hemoglobin
MCHC	Mean corpuscular hemoglobin concentration

MCV	Mean corpuscular volume
Mg	Milligram
mL	Milliliter
MNWS	Minnesota Nicotine Withdrawal Scale
PHQ-9	The Patient Health Questionnaire
PPM	Parts per million
RBC	Red blood cell
RCT	Randomized Control Trial
RRC	Rose Research Center, LLC.
SaaS	Software-as-a-Service
SAE	Serious adverse event
SMS	Short Message Service
SOP	Standard operating procedure
SSL	Secure Sockets Layer
STAI	State-Trait Anxiety Inventory
TLS	Transport Layer Security
WBC	White blood cell
WHO	World Health Organization
WI-PREPARE	The Wisconsin Predicting Patients' Relapse Questionnaire

# 1 INTRODUCTION

---

## 1.1 STUDY DESIGN AND PLAN

This open-label study will explore the impact of combination zonisamide and bupropion on the process of switching from combustible cigarettes (CC) to an e-cigarette.

Zonisamide is an FDA-approved medication with an anti-seizure indication, with daily doses usually ranging from 100 mg/day to 600 mg/day). It has multiple mechanisms of action, which include inhibiting activation of voltage-gated sodium channels at therapeutic levels. In addition, zonisamide also inhibits glutamate-mediated neurotransmission and enhances inhibitory GABA-ergic as well as serotonergic neurotransmission. It also enhances dopamine levels in the striatum, which in theory could help replace the desired effects of addictive drugs such as nicotine that also raise striatal dopamine. Topiramate, a drug sharing some actions with zonisamide, has been shown to facilitate smoking cessation and prevent post-cessation weight gain. Zonisamide has been shown to reduce ad libitum smoking as well as to relieve craving for cigarettes. It also has been shown to decrease anger, restlessness and impatience during smoking abstinence.

The zonisamide/bupropion combination has an additional rationale in that the potential side effects of each agent are offset by the other. For example, bupropion is associated with side effects of agitation and insomnia while zonisamide has sedative properties. Conversely, the side effects of zonisamide include sedation, which are expected to be partially offset by bupropion's stimulant actions. The combination of bupropion and zonisamide has been shown to be well tolerated in studies of weight loss produced by this drug combination.

There is no therapeutic intent in that smokers' nicotine/tobacco dependence will not be treated; the goal is to switch from one form of nicotine/tobacco dependence (CC) to dependence on a different tobacco product (e-cigarettes).

## 1.2 BACKGROUND

According to the U.S. Surgeon General (2010 Report), the major smoking-related diseases, including cancer, heart and lung disease, have been linked to inhaling the combustion products of burning tobacco, rather than to nicotine per se. Therefore, less toxic forms of nicotine delivery, such as e-cigarettes, offer a potential avenue for harm reduction for smokers who cannot or do not wish to relinquish their nicotine dependence. A substantial fraction of smokers who use e-cigarettes continue to smoke combustible cigarettes ("dual use"), eroding the potential beneficial impact on disease risk. Therefore, it is important to examine strategies for enhancing complete switching to e-cigarettes from combustible cigarettes. We hypothesize that dual users find it most difficult to relinquish their favorite cigarettes, which surveys indicate are those smoked after meals. We hypothesize that a specific combination of FDA-approved medications shown to promote weight loss, consisting of bupropion and zonisamide, will reduce appetite, reduce the enjoyment of cigarettes after meals, and facilitate complete switching from combustible cigarettes to e-cigarettes. In addition to the hypothesized mechanism of reducing post-meal enjoyment of smoking, bupropion is an FDA-approved smoking cessation treatment (at 150 mg b.i.d.) that reduces craving for cigarettes as well as withdrawal symptoms of irritability, which could also facilitate complete switching. Bupropion and its metabolites block reuptake of dopamine and norepinephrine, which also have anti-depressant effects.

## 2 STUDY OBJECTIVES AND ENDPOINTS

### 2.1 COMPLETE SWITCHING FROM CC TO HALO G6

The primary switching outcome will be smoking abstinence during weeks 8-11 post-quit date. This will be defined as self-report of no cigarette smoking (not even a puff), confirmed by an expired air CO reading of less than 5 ppm.

### 2.2 POINT ABSTINENCE (FROM CC) AT SIX MONTHS POST SWITCH

A secondary outcome will be 7-day point abstinence at 6 months post-switch, for participants who are smoking abstinent during weeks 8-11 post-quit, as defined above in Section 2.1. This will be assessed by self-report utilizing an automated SMS messaging system.

### 2.3 CHANGE IN REWARDING EFFECTS OF SMOKING CIGARETTES

Secondary analyses will evaluate the hypothesis that enjoyment of smoking after meals is attenuated by zonisamide/bupropion treatment. The smoking satisfaction scale of the mCEQ-E will be compared between cigarettes smoked after meals versus all others smoked during the day, examining how this difference changes after zonisamide/bupropion usage. Additionally, the proportion of participants who report smoking after meals, while reporting not smoking at other times, will be compared between the first week and the weeks after zonisamide/bupropion usage.

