## 8.6 SMS MESSAGING

8.6.1 Daily SMS Message (after screening, prior to V2) – Participants will receive a text with a link to a survey to access the following:

- Have you smoked any combustible cigarettes today?
  - If yes, how many cigarettes did you smoke?
  - What was your favorite cigarette of the day?  
1-First one, 2-One immediately after a meal, 3-Any other cigarette

8.6.2 Daily SMS Message (From Visit 2) -- Participants will receive a text with a link to a survey to assess the following:

- Have you smoked any combustible cigarettes today?
  - If yes, how many cigarettes did you smoke?
  - Which cigarette did you smoke today? (If only 1 cigarette is reported)  
1-First one of the day, 2-One immediately after a meal, 3-Any other cigarette
  - What was your favorite cigarette of the day? (Of more than 1 cigarette is reported)  
1-First one, 2-One immediately after a meal, 3-Any other cigarette
- Have you used your e-cigarette today?
  - If yes, how many times did you use your e-cigarette today?
- Did you take your study drugs this morning? (After Visit 3)

8.6.3 6-Month follow up SMS Message -- Participants will receive a text with a link to a survey to assess the following:

- Have you smoked a combustible cigarette since your last visit?
  - If yes, are you still smoking combustible cigarettes right now?
  - How many combustible cigarettes do you smoke per day on average?
- Have you used an e-cigarette since your last visit?
  - If yes, are you still using an e-cigarette?
  - How often do you use an e-cigarette?
- Have you used any other nicotine containing products (other than e-cigarettes) since you last visit?

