Appendix 9 – modified Cigarette Evaluation Questionnaire - Ext (mCEQ-E)

### CIGARETTE EVALUATION QUESTIONNAIRE- Ext modified

Have you smoked any cigarettes since your last visit?

- No: Skip questionnaire
- Yes: Please answer the following questions based on the **FIRST** cigarette you smoked on the last day you smoked.

	Not at all	Very little	A little	Moderately	A lot	Quite a lot	Extremely
1. Was it satisfying?							
2. Did it taste good?							
3. Did it make you dizzy?							
4. Did it calm you down?							
5. Did it help you concentrate?							
6. Did it make you feel more awake?							
7. Did it reduce your hunger for food?							
8. Did it make you nauseated?							
9. Did it make you feel less irritable?							
10. Did you enjoy the sensations of the smoke in your throat and chest?							
11. Did it immediately reduce your craving for cigarettes?							

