12. Did you enjoy smoking?							

Please answer the following questions based on the cigarette smoked **immediately after a meal**.

- Did not smoke **immediately after a meal**: Skip section

	Not at all	Very little	A little	Moderately	A lot	Quite a lot	Extremely
1. Was it satisfying?							
2. Did it taste good?							
3. Did it make you dizzy?							
4. Did it calm you down?							
5. Did it help you concentrate?							
6. Did it make you feel more awake?							
7. Did it reduce your hunger for food?							
8. Did it make you feel nauseated?							
9. Did it make you feel less irritable?							

10. Did you enjoy the sensations of the smoke in your throat and chest?							

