11. Did it immediately reduce your craving for cigarettes?							
12. Did you enjoy smoking?							

Please answer the following questions regarding **all other cigarettes smoked** on the last day you smoked.

	Not at all	Very little	A little	Moderately	A lot	Quite a lot	Extremely
1. Was it satisfying?							
2. Did it taste good?							
3. Did it make you dizzy?							
4. Did it calm you down?							
5. Did it help you concentrate?							
6. Did it make you feel more awake?							
7. Did it reduce your hunger for food?							
8. Did it make you nauseated?							
9. Did it make you feel less irritable?							
10. Did you enjoy the sensations of the smoke in your throat and chest?							

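### The after-meal-only proportion in Section 2.3 cannot be established on days with two or more cigarettes, because no planned item shows that none was smoked at other times

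*Combined protocol and SAP*

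**What the plan says.** Section 2.3 sets two secondary analyses of smoking after meals. The first compares mCEQ-E satisfaction scores by occasion. The second, at issue here, is that "the proportion of participants who report smoking after meals, while reporting not smoking at other times, will be compared between the first week"; the other side of the comparison is the period once study drug has started. The section names no instrument, time unit or classification rule for this second analysis, and Section 13.1.2 gives no derivation.

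Three planned sources touch on the occasion of smoking:

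- **Daily text message from V2 (Section 8.6.2).** The occasion item is conditional: "Which cigarette did you smoke today? (If only 1 cigarette is reported". Its options are "1-First one of the day, 2-One immediately after a meal, 3-Any other cigarette". On heavier days it is replaced by "What was your favorite cigarette of the day? (Of more than 1 cigarette is reported".
- **Daily text message before V2 (Section 8.6.1).** It asks whether any cigarettes were smoked, how many, and which was the favorite. It has no occasion item.
- **mCEQ-E (Appendix 9), given at V2 to V7 (Section 8.5).** Every smoker rates the first "cigarette you smoked on the last day you smoked". The after-meal part opens with the box "Did not smoke immediately after a meal: Skip section". The part on "all other cigarettes smoked on the last day you smoked" has no such box.

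Section 3.1 places the start of study drug at V3, after the first week of e-cigarette use. Section 4.1.1 requires at least 10 cigarettes per day at entry.

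**The concern.** The proportion needs two reports from each participant: that they smoked after meals, and that they did not smoke at any other time. The first is at least partly collected. The second appears to be collected only on days with exactly one cigarette.

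Section 1.2 puts forward reduced enjoyment of after-meal cigarettes as a mechanism of the drug combination, and this analysis bears on it. If qualifying days are missed more often when more cigarettes are smoked, the loss can differ between the periods compared. Part of any change would then come from the questionnaire. Occasions that were not asked about on the day cannot be recovered afterwards.

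**Working it through.** The documents give no rate, sample size or power for this proportion, so there is no figure to reproduce. The check has two parts: what each item can establish, and an illustration of the size.

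**1. What each item can establish**

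- *Text message, one cigarette.* An answer of option 2 establishes after-meal-only smoking. But a day's only cigarette is also its first, so options 1 and 2 can both be true. If a fraction f of qualifying days is answered with option 1, every recorded figure is multiplied by (1 − f). f is unknown.
- *Text message, two or more.* A favorite after a meal says nothing about the other cigarettes. A favorite at some other time can rule the day out. No answer can rule it in.
- *Text message before V2.* No day can be ruled in.
- *mCEQ-E.* It covers only the last smoking day before the visit. The first cigarette's relation to a meal is not recorded. A blank all-other part could mean no such cigarettes or an unanswered section, and no rule says which.
- *FTND, ABOUT, Reasons to Smoke and the 6-month message.* None records the meal timing of the cigarettes smoked.

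**2. Size, under assumptions that are not in the documents**

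Let the daily count be Poisson with mean L, and let each cigarette independently follow a meal with probability s (0.2 to 0.5 assumed). Write m = sL for mean after-meal cigarettes per day.

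- True after-meal-only share of days: t = exp(−(1−s)L) − exp(−L)
- Share that the text message can record: g = sL·exp(−L)
- Capture: g/t = m/(exp(m) − 1). For m = 1.0 this is 1/(2.718 − 1) = 58%.

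| L per day | s | m | True t | Recordable g | Capture |
|---|---|---|---|---|---|
| 1 | 0.2 | 0.2 | 8.15% | 7.36% | 90% |
| 1 | 0.5 | 0.5 | 23.87% | 18.39% | 77% |
| 3 | 0.2 | 0.6 | 4.09% | 2.99% | 73% |
| 3 | 0.5 | 1.5 | 17.33% | 7.47% | 43% |
| 5 | 0.2 | 1.0 | 1.16% | 0.67% | 58% |
| 5 | 0.5 | 2.5 | 7.53% | 1.68% | 22% |

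**3. Effect on the comparison when consumption and after-meal share both fall**

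| Counts | L | s | True | Recordable |
|---|---|---|---|---|
| Poisson | 5 to 3 | 0.50 to 0.25 | 7.53% to 5.56% | 1.68% to 3.73% |
| Negative binomial, size 5 | 5 to 3 | 0.50 to 0.25 | 10.04% to 6.06% | 3.91% to 4.47% |
| Negative binomial, size 2 | 5 to 3 | 0.50 to 0.25 | 11.59% to 6.15% | 5.83% to 4.80% |
| Poisson | 5 to 3 | 0.30 to 0.15 | 2.35% to 2.83% | 1.01% to 2.24% |
| Poisson | 6 to 3 | 0.50 to 0.25 | 4.73% to 5.56% | 0.74% to 3.73% |

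In the last row, 0.74% is 0.5 × 6 × exp(−6). The direction reverses in the first two rows only. In the third, a 47% fall is recorded as an 18% fall. In the fourth, a 1.20-fold rise (2.83/2.35) is recorded as 2.22-fold (2.24/1.01).

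**4. How much belongs to the endpoint itself**

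The chance of at least one after-meal-only day in a week is 1 − (1 − p)^7, where p is t or g. With s held constant between 0.2 and 0.5:

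| | 10 per day | 1 per day |
|---|---|---|
| Perfect recording | 0.2% to 4.6% | 45% to 85% |
| Text message as planned | 0.06% to 0.16% | 41% to 76% |

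Most of the movement is present even with perfect recording.

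**The case against.** **The instrument is not assigned.** The preceding sentence of Section 2.3 names the mCEQ-E. Comparing the V3 form with the V4 to V7 forms is a natural reading, and that form is not restricted to one-cigarette days. This stands: the capture percentages apply only to a text-message derivation. It does not rescue the endpoint, because the mCEQ-E cannot show exclusivity either, for the reasons given in the check.

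**The one-cigarette item may serve another purpose.** It could be meant to identify the last cigarette that a dual user keeps, in line with Section 1.2. It can do that, and this is a reason to keep it. Section 2.3, however, does not limit its proportion to one-cigarette days.

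**Tempting stronger readings.** A reader might infer that the planned items would turn a real fall into a recorded rise. The documents do not support that as a general statement. In the scenarios tried, the reversal appears at 5 cigarettes per day with half of them after meals. It disappears at 6 per day, at a 30% share, or with more variable counts. Nor does any section tell participants to cut down between V2 and V3; e-cigarette use that week is ad libitum. If they still smoke 10 per day then, the true share is only 0.03% to 0.67% of days, so there is almost nothing to fall from.

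A reader might also take all dependence on cigarettes per day as a recording fault. Most of it is a property of the endpoint.

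**Conclusion.** The concern holds in a limited form. The planned items, used exactly as written, cannot positively establish after-meal-only smoking on days with two or more cigarettes, and are ambiguous even on days with one. This follows from the wording of the items alone and needs no assumption.

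The size does rest on assumptions: Poisson counts, independent occasions, a 20% to 50% after-meal share, and the text message as the source. On those, capture runs from about 90% at 0.2 mean after-meal cigarettes per day to 22% at 2.5, so the under-recording varies with consumption. At low counts with a 20% share the effect is small.

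The severity is low. This is one clause of a secondary analysis in a single-group pilot of 25 to 50 participants. The switching thresholds in Sections 3.1.1 to 3.1.3 do not use it.

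**What to change.** Keep the existing text-message items; the one-cigarette item also holds information on first-of-day smoking that would be lost if it were replaced. From V2, on every day with at least one cigarette, add a question asking how many of that day's cigarettes were smoked immediately after a meal. A day is after-meal-only when this count equals the daily total and is at least one. This also settles the overlapping options on one-cigarette days.

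In Section 2.3:

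- name this item as the source;
- define how a participant is classed in a week (for example, at least one after-meal-only day) and how unanswered days are treated;
- state that the first week runs from V2 to V3, the reading that Section 3.1 supports;
- report the proportion alongside cigarettes per day, and do not read a change in the raw proportion alone as a change in after-meal smoking.

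A box on the mCEQ-E for no smoking at other times is optional. It cannot establish exclusivity unless the form also records whether the first cigarette followed a meal.

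The cost is one short extra question on smoking days and a few sentences of text, with no new visit or instrument. The proportion will still depend partly on cigarettes per day.

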## 3 INVESTIGATIONAL PLAN

### 3.1 OVERALL STUDY DESIGN AND PLAN

This single-group, small-scale, open-label study (N= 25 to 50) will evaluate the impact of combination zonisamide and bupropion on the process of switching from combustible cigarettes (CC) to an e-cigarette. There will be a data collection period of at least five days to obtain baseline data on use of combustible cigarettes. Participants enrolled in the study will receive a G6 e-cigarette at V2 for *ad libitum* use. After the first week of e-cigarette use, (at V3) participants will be given zonisamide (100 mg/daily) and will begin extended-release bupropion dosing (150 mg each morning days 1-3, then 300 mg/daily) in addition to continued use of the G6. At each visit, participants will receive enough zonisamide, bupropion, and Halo G6 cartomizers to last until their next study visit. Halo G6 and combination zonisamide and bupropion use will continue until the participant returns for the End-of-Study visit (V7).

[figure not shown]

Figure 1 - Overall Study Design

The outcome of the combination zonisamide and bupropion on the process of switching from combustible cigarettes (CC) to an e-cigarette will be compared to the following benchmarks. Initial results will fall into one of the following three categories:

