#### 4.1.1 Inclusion Criteria

Each participant must meet all the following inclusion criteria before enrollment:

Inclusion Criteria
1. Has signed the ICF and is able to read and understand the information provided in the ICF.
2. Is 21 to 65 years of age (inclusive) at screening.
3. Smokes at least 10 commercially available cigarettes per day (no brand restrictions), for the last 12 months.
4. Has an expired air CO reading of at least 10 ppm at screening.
5. Interested in switching to an electronic cigarette.
6. Willing and able to comply with the requirements of the study.
7. Owns a smart phone with text message and data capabilities compatible with necessary surveys.

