### How do I take this medicine?

1. Take zonisamide exactly as directed. The blister packs are designed to help you take the medicine properly.
  - a. Take 2 capsules (50 mg each, total of 100 mg) in the morning.
  - b. Only change your medicine at the direction of the study personnel or if you have a serious concern.
2. Do not take this medicine if you have a severe allergy to sulfa drugs (like Bactrim, Septra, Diabeta).
3. Do not crush, chew, open or split the capsule.
4. Take zonisamide with a full glass (8 ounces) of water. Zonisamide can be taken with or without food (do NOT drink alcohol with zonisamide).
5. We will schedule you to start taking zonisamide about 7 days before your actual switch date (the day you stop smoking and only use the electronic cigarette).
6. If you forget to take a dose of zonisamide, take it as soon as you remember. If it is almost time for your next dose (less than 6 hours), just wait and take your next dose at the regular time. Do NOT take an extra dose to make up for the dose you forgot.
7. Keep this medication in a safe place, AWAY FROM CHILDREN. It should be stored at room temperature (not in your car) and away from direct sun, excessive heat, cold, or moisture. You MUST return any unused medication.

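### Section 2.3 compares the after-meal-only proportion across the switch day, so a rise is likely as total smoking falls, even if the drugs reduce after-meal smoking

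*Combined protocol and SAP*

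**What the plan says.** Section 2.3 sets out secondary analyses of the hypothesis that "enjoyment of smoking after meals is attenuated by zonisamide/bupropion treatment". Its lead analysis uses the mCEQ-E satisfaction scale, after-meal cigarettes against the others. It then adds a second measure, "the proportion of participants who report smoking after meals, while reporting not smoking at other times", which "will be compared between the first week and the weeks after zonisamide/bupropion usage". No test, expected direction, scoring rule or adjustment for cigarettes per day is given for this second measure, and section 13.1.2 does not mention it.

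The two periods have to be pieced together from elsewhere:

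- Entry (section 4.1.1, item 3): "Smokes at least 10 commercially available cigarettes per day (no brand restrictions), for the last 12 months".
- Drug start (section 3.1): "After the first week of e-cigarette use, (at V3) participants will be given zonisamide (100 mg/daily".
- Switch day (participant instructions for zonisamide, with matching text for bupropion): drugs begin "about 7 days before your actual switch date (the day you stop smoking and only use the electronic cigarette".
- Durations: 13 weeks of G6 use (section 5.3) and 12 weeks of dosing (section 6.2).

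The study has a single group of 25 to 50 participants (section 3.1).

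**The concern.** Section 1.2 gives the rationale that "dual users find it most difficult to relinquish their favorite cigarettes, which surveys indicate are those smoked after meals". If the drugs weaken the appeal of those cigarettes, smoking only after meals should become less common, other things equal. Other things are not equal. The first period is ad libitum smoking in people enrolled as smokers of 10 or more a day, few of whom can be smoking only after meals. The second period is mostly time after they were told to stop. Someone who smokes one or two cigarettes a day will have days on which every cigarette happens to follow a meal, with no change in how rewarding such cigarettes are.

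The comparison therefore mixes any drug effect on after-meal smoking with the fall in total smoking that the trial sets out to produce. There is no control group to separate them. A rise could be reported as evidence against the mechanism on which the combination was chosen. The problem would remain even if the occasion of every cigarette were recorded perfectly.

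**Working it through.** The documents state no rate or power for this measure, so there is no figure to reproduce.

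**Timeline.** 13 weeks of G6 use minus 1 G6-only week gives 12 drug weeks. Minus about 1 week before the switch day leaves about 11 post-switch weeks. This fits the primary window of weeks 8-11 after the quit date (section 2.1). The first week is not formally defined, but the 5-day baseline, the G6-only week and the first drug week all come before the switch day.

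**Model (assumed).** Cigarettes per day are Poisson with mean L, and each is an after-meal cigarette with probability q. Then:

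- P(after-meal-only day): p = exp(-L(1-q)) - exp(-L)
- P(at least one such day in a week) = 1 - (1-p)^7
- P(smoked in the week, and only after meals all week) = exp(-7L(1-q)) - exp(-7L)

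The documents give neither q nor consumption in any study week. The values below are illustrations.

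| L per day | q | p | At least one day in a week |
|---|---|---|---|
| 12 | 0.25 | exp(-9) - exp(-12) = 0.0001 | 0.1% |
| 10 | 0.25 | exp(-7.5) - exp(-10) = 0.0005 | 0.4% |
| 8 | 0.25 | exp(-6) - exp(-8) = 0.0021 | 1.5% |
| 5 | 0.25 | exp(-3.75) - exp(-5) = 0.0168 | 11% |
| 3 | 0.25 | exp(-2.25) - exp(-3) = 0.0556 | 33% |
| 1 | 0.25 | exp(-0.75) - exp(-1) = 0.1045 | 54% |
| 1 | 0.125 | exp(-0.875) - exp(-1) = 0.0490 | 30% |

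**Sensitivity to q.** At 1 a day, q from 0.20 to 0.30 gives 45% to 62% with no drug effect, and 24% to 35% with q halved.

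**Abstainers.** The wording suggests all participants as denominator, and abstainers score zero. The plan's own rates are 45% (benchmark, section 13.1.1) and 64% (advance threshold, section 3.1.1). With q halved and the rest at 1 a day: 0.296 x 0.55 = 16%, and 0.296 x 0.36 = 11%.

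**Whole-week scoring.** At 1 a day: exp(-5.25) - exp(-7) = 0.4% for q = 0.25, and exp(-6.125) - exp(-7) = 0.1% for q = 0.125. At 0.2 a day: exp(-1.05) - exp(-1.4) = 10%, and exp(-1.225) - exp(-1.4) = 5%. At 10 a day it is effectively zero.

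**Equal consumption.** Among one-cigarette days, the chance that the cigarette followed a meal is simply q. A halving then shows as a fall, 0.25 to 0.125. The rise in the planned contrast comes from L, not from q.

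**The case against.** Four points on the other side have force.

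1. The plan does not say how a participant is scored over a week. The 30% and 54% figures need the rule of at least one after-meal-only day. Under whole-week scoring at 1 a day they shrink to 0.1% and 0.4%. This stands: the size is not fixed by the documents.
2. Not everyone goes on smoking after the switch. Counting abstainers as zero cuts 30% to about 16% or 11%, and complete abstinence brings the proportion back to zero. This stands.
3. The entry criterion describes the 12 months before screening, while the first week is already a week of free G6 use in people interested in switching. At 5 or 3 a day the starting value is 11% or 33%. Against 11% to 16% afterwards, the result could be flat or a fall. This also stands, though such a result would still depend on consumption.
4. The measure is subsidiary. It plays no part in the advance-or-stop rule (sections 3.1.1 to 3.1.3).

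Two stronger readings are tempting. A reader might infer that the proportion cannot fall and must climb from 0% to about 30%. The documents do not support that, for the first three reasons. A reader might also infer that section 2.3 cannot address its hypothesis at all. That does not follow either, because the mCEQ-E contrast compares satisfaction ratings between types of cigarette and is not affected by this point.

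None of this removes the core: the two periods lie mostly on opposite sides of the switch day, and nothing adjusts for how much is smoked.

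**Conclusion.** The point holds as a confounded comparison with a likely, not certain, upward bias. A low starting value rests on first-week smoking staying near the entry level. The later rise rests on residual smoking of a few cigarettes a day or fewer in those who have not fully switched. Under the day-in-a-week scoring and q = 0.25, a drug effect that halves the after-meal share appears as a change from 0.4% or less (10 to 12 a day) to 30% at 1 a day, or to about 11% to 16% with abstainers counted. Whole-week scoring gives far smaller figures at 1 a day, and a large drop in smoking during the first week could remove or reverse the rise. In none of these cases does the direction of change isolate an effect on after-meal smoking, so the result should not be read for or against the mechanism. The primary outcome is untouched. The change is worth making because the result could mislead and the remedy is cheap.

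**What to change.** In section 2.3, drop the inferential comparison of the after-meal-only proportion with the first week. Report it week by week, with its scoring rule and denominator stated, as a description of residual smoking.

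Add a within-participant comparison of two periods before the switch day: the G6-only week (V2 to V3) and the drug days from V3 to the switch day. The measure is the share of days on which the after-meal cigarette is named the favorite, among days with more than one cigarette reported. That denominator is needed because section 8.6.2 asks "What was your favorite cigarette of the day? (Of more than 1 cigarette is reported", so one-cigarette days have no favorite answer. Summarise those days separately from the item asking which cigarette was smoked. Use the 5-day baseline (section 8.6.1) as a second reference, limited to the same kind of day, since the favorite item there carries no such condition.

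The cost is wording, plus recording each participant's switch date, which has no row in the section 8.5 schedule. The SMS questions stay as they are. The downside is precision: the drug window is only about 7 days and includes the first 3 days of bupropion at the initial dose, so the comparison is imprecise and may understate an effect. It also remains an uncontrolled before-and-after comparison.
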